2.3.3 MS baseline disease characteristics

MS baseline characteristics, MS disease history and MS medication history will be summarized for the FAS. MS baseline characteristics include baseline EDSS, 9HPT, T25FW, CCL LCVA, key MRI parameters (e.g., number of Gd-enhancing T1 lesions, number of T2 lesions, T2 lesion volume), Biomarkers such as NfL and IgG, IgM, CD-19 B-cell counts, Lymphocytes and neutrophils.

Baseline lymphocyte and neutrophil values should also be summarized, including reporting of lymphocyte and neutrophil abnormalities (Table 2-12).

Of note, laboratory values below limit of quantification (e.g. value coded as <x.xx) will be imputed to the lower limit of quantification/2. MS baseline disease characteristics will also be summarized by last prior DMT.

Table 2-12 Notable abnormalities for lymphocyte and neutrophil counts

Lymphocytes (10E9 /mL)	Decrease in lymphocytes counts: Gr1: <lln -="" 0.2="" 0.5="" 0.8="" 10e9="" <0.5="" <0.8="" gr2:="" gr3:="" l="" l<="" th="" x=""></lln>
	Gr4: <0.2 x 10E9/L Increase in lymphocytes counts: >4.0 - 20 x 10E9 /L (grade 2 lymphocytosis) >20 x 10E9 /L (grade 3 lymphocytosis)
Neutrophils (10E9 /mL)	Decrease in neutrophils counts: Gr1: <lln -="" 0.5="" 1.0="" 1.5="" 10e9="" <0.5="" <1.0="" <1.5-="" gr2:="" gr3:="" gr4:="" l="" l<="" td="" x=""></lln>

MS disease history includes duration of MS since diagnosis (years), duration of MS since first symptom (years), number of relapses in the last 12 months prior to screening, number of relapses in the 12 to 24 months prior to screening, type of MS at study entry (i.e., RRMS or SPMS), time since onset of SPMS, time since onset of most recent relapse (months), and number of prior DMTs.

Duration of MS since diagnosis (years) will be derived [(first dose date – MS diagnosis start date + 1)/365.25]; duration of MS since first symptom (years) will be derived as [(first dose date – first MS symptom date +1)/365.25]; time since onset of SPMS (years) will be derived as [(first dose date – conversion to SPMS date +1)/365.25]; and time since onset of most recent relapse (months) will be derived as [(first dose date – most recent relapse onset date + 1)/(365.25/12)]. In these calculations, partial dates if any will be imputed according to the rules specified in Section 5.1.4.1.

MS medication history of previous disease-modifying drugs (coded by WHO drug dictionary) will be summarized by preferred term (PT).

Consider following categories to summarize disease history variables:

- Duration of MS since diagnosis (years): 0-<1, 1-<2, 2-<5, 5-<10
- Duration of MS since first symptom (years): 0-<1, 1-<2, 2-<5, 5-<10, 10-<15, >=15
- Number of relapses in the last 12 months prior to screening: 0, 1, 2-3, 4-5, >5
- Number of relapses in the 12 to 24 months prior to screening: 0, 1, 2-3, 4-5, >5
- Type of MS at study entry: RRMS, SPMS
- Number of prior DMTs: 1, 2, 3

MS disease history will also be summarized by last prior DMT.

2.3.4 Medical history

Medical history will be summarized for the FAS. Any condition entered on the Medical History (MH) CRF will be coded using the MedDRA dictionary. The medical history will be summarized by primary system organ class (SOC) and preferred term (PT).

2.4 Treatments (study treatment, rescue medication, concomitant therapies, compliance)

2.4.1 Study treatment / compliance / time at risk

Duration of exposure to study drug will be derived as follows:

• For subjects on ofatumumab treatment, duration of exposure will be calculated as (last injection date – first injection date + 31 – Σ [(j+1)th injection date – jth injection date – 31]), where j and j+1 refer to consecutive injections with injection dates more than 31 days apart (as subjects are scheduled to take the subcutaneous injections every 28 +/- 3 days).

Duration of exposure to study drug will be summarized descriptively on SAF set by duration category (i.e., ≥ 1 week, ≥ 2 weeks, ≥ 4 weeks, ≥ 8 weeks, ≥ 12 weeks, ≥ 24 weeks, ≥ 24 weeks, ≥ 48 weeks, ≥ 60 week

The number of subject-years is calculated as (the sum of the number of days of exposure for all subjects)/365.25 and will be summarized.

Compliance to the study drug administration schedule will be calculated as duration of exposure to study drug in (days)/duration of on-treatment period (as defined in Section 2.1.1) in (days) $\times 100\%$. This rule means that compliance will be measured during the time interval the subject took study medication: premature discontinuation from study drug will not be considered non-compliance. Compliance to study drug administration will be summarized descriptively on SAF. In addition, compliance will be summarized with cumulative number and percentage of subjects in each compliance category (i.e., $\geq 20\%$, $\geq 30\%$, $\geq 40\%$, $\geq 50\%$, $\geq 60\%$, $\geq 70\%$, $\geq 80\%$, $\geq 90\%$, $\geq 95\%$, $\geq 98\%$, = 100%).

Time at risk: Time at risk for AE and time at risk for SAE will be summarized in a similar way to duration of exposure to study drug. Intermediate treatment interruptions will be included in time-at-risk calculations. It will be derived as follows:

Time at risk for AE is defined as the number of days spent in the study, from first to last administration of study drug, plus the safety data cut-off as described in Section 2.1. Same definition is used for time at risk for SAE.

Dose interruptions due to COVID-19 pandemic: Summary of at least one missed dose of ofatumumab due to non COVID-19 related reasons, COVID-19 related reasons and overall will be provided. Further frequency and percentage of subjects missed number of doses in the following category will be provided: 1-3, 4-6, 7-9, >9. Here subject may be counted in more than one category.

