4.2 Rationale for dose/regimen and duration of treatment

Ofatumumab dose

The dose regimen for ofatumumab for this study is a *loading dose regimen* of 20 mg at Day 1, Day 7 and Day 14, followed by a monthly *maintenance dose regimen* of 20 mg administered every 4 weeks, starting at week 4.

This dose regimen is consistent with the dose and regimen in the Phase 3 development program of ofatumumab in RMS.

Duration of treatment

Treatment duration within the study will be 96 weeks with the primary endpoint being at 96 weeks.

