Subjects should be instructed to record any missed doses in the subject diary provided for the study and to inform the study staff of any missed s.c. injection(s). This can be done at the visits and/or during the monthly remote contacts that are scheduled throughout the study during which, the study site staff will inquire about the subject's status and compliance with study treatment administration or issues related to the home administration.

Subjects who miss s.c. injections or temporarily interrupt study drug without discontinuing from the study or withdrawing consent, will be permitted to resume study drug if determined to

be safe and appropriate in the opinion of the investigator. When resuming study drug, the timing of the next s.c. injection will be determined based on the original study schedule as followed:

- If one monthly injection is missed by 1 week or less, the subject should take injection as soon as possible. The next injection should then be administered according to the original schedule.
- If one monthly injection is missed by more than 1 week, the subject should skip the dose and take the next dose at the time when the next injection would be due according to the original schedule.
- If two or more consecutive monthly injections are missed, the Investigator should inform the Sponsor before re-starting dosing.

Information about all kits of study medication assigned by the IRT will be recorded in the IRT system.

A subject will be provided with the injection instruction leaflet, which includes detailed information, precautions and instructions for administering s.c. injections using the AIs. This information should be reviewed with the subject (and his/her partner/relative as applicable) to ensure that they understand the correct procedure for self/home administration.

7 Informed consent procedures

The Investigator or his/her representative will explain the nature of the study, including the risks and benefits, to the subject or their legally authorized representative and answer all questions regarding the study.

Subjects must be informed that their participation is voluntary. Subjects or their legally authorized representatives will be required to sign a statement of informed consent that meets the requirements of 21 CFR 50, local regulations, ICH guidelines, privacy and data protection requirements, where applicable, and the IRB/IEC or study center.

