2.1.1 General definitions

Below some general definitions to be used in the rest of the document are summarized.

Table 2-1 General Definitions

Table 2-1 General Deminitions	
Study treatment/Study drug	The investigational drug (ofatumumab) will be referred as study treatment or study drug.
Date of first administration of study drug/first dose date	The first dose date of active study drug administration.
Date of last administration of study drug/last dose date	The last dose date of active study drug administration.
Study Day 1 or Day 1	The date of first administration of study drug/first dose date.
Study Day	 All other study days will be labeled relative to Day 1. For events with dates on or after Day 1, study day for the event is calculated as (event start date – first dose date + 1). For events with dates before Day 1, study day for the event is calculated as (event start date – first dose date). Day 0 will not be used.
Duration of an event	Duration of an event is calculated as (event end date – event start date +1).
1 month	30 days; to be used in defining 6-month confirmed disability worsening or improvement.
4 weeks	28 days; to be used in determining target days of scheduled visits. It is based on the scheduled injection frequency for ofatumumab (during the maintenance phase).
Day post-study drug discontinuation	Day post-study drug discontinuation for a particular event is calculated as (event start date – study drug discontinuation date).
Baseline	Baseline is the last assessment obtained prior to the first administration of study drug. No visit windows will be needed for the identification of baseline assessment.
	For pulse and blood pressure vital sign values, the baseline is the average of the non-missing values of the 3 measurements taken on the last visit prior to the first administration of study drug. The pre-injection assessment values on Day 1 vital sign case report form (CRF) page will not be used for baseline derivations.

On-treatment period	On-treatment period includes days from the first injection date until 30 days after the last injection date. This definition considers subjects on ofatumumab are scheduled to inject every 28 +/- 3 days. For calculation of compliance to study drug administration, similar definition of on-treatment period will be used.

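### The SAP's compliance percentage cannot register missed Day 7 or Day 14 loading doses: an otherwise adherent subject who misses both is reported as 100% compliant

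*SAP*

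**What the plan says.** Protocol 4.2 sets a loading regimen of "20 mg at Day 1, Day 7 and Day 14", followed by one dose every 4 weeks from Week 4.

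SAP 2.4.1 builds compliance in two steps.

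- **Exposure.** The formula begins "duration of exposure will be calculated as (last injection date – first injection date + 31" and then subtracts, for each qualifying pair of injections, the days by which their gap exceeds 31. Qualifying pairs are defined by the phrase "where j and j+1 refer to consecutive injections with injection dates more than 31 days apart". The reason given for 31 days is "as subjects are scheduled to take the subcutaneous injections every 28 +/- 3 days".
- **Compliance.** This is "duration of exposure to study drug in (days)/duration of on-treatment period (as defined in Section 2.1.1) in (days"), times 100%. SAP 2.1.1 supplies the denominator: "On-treatment period includes days from the first injection date until 30 days after the last injection date".

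Compliance is summarised on the Safety Set, both descriptively and in cumulative categories ending in a row for exactly 100%. A later paragraph of SAP 2.4.1, on dose interruptions, plans a "Summary of at least one missed dose of ofatumumab due to non COVID-19 related reasons", for COVID-19 reasons and overall, with missed doses grouped as 1-3, 4-6, 7-9 and more than 9.

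**The concern.** SAP 2.4.1 presents this percentage as compliance with the schedule of study drug administration, and that schedule includes the loading doses. The 31-day allowance fits monthly dosing. In the loading phase the doses are about a week apart, and the whole span from Day 1 to Week 4 is shorter than the allowance. Leaving out the doses in between creates no gap that the formula can see.

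This is a single-arm effectiveness trial, so readers will use the compliance table to judge whether the stated regimen was given. They will take the 100% row to mean fully dosed. As defined, that row mixes subjects who had every loading dose with subjects who had only the first.

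**Working it through.** **Inputs**

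- Loading doses on Days 1, 7 and 14 (Protocol 4.2).
- Maintenance every 28 days from Week 4. Table 8-1 places the Week 4 visit at Day 28 ± 1; Protocol 6.7.2 allows ± 3 days for monthly injections.
- Last dose taken as Day 644, with Day 672 as a variant. Doses due to Day 644: 3 loading plus 644/28 = 23 monthly, 26 in all; to Day 672, 27.

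**Formulas**

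- Exposure = last − first + 31 − Σ(gap − 31), summed over gaps above 31 days.
- On-treatment period = last − first + 30 + 1 = last − first + 31, counting both end days.
- Compliance = exposure / on-treatment period.

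The leading terms of the numerator equal the denominator, so any subject with no gap above 31 days scores exactly 100%. The documents give no worked figure to reproduce; the fully adherent schedule serves as the check.

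**Results, last dose Day 644** (644 − 1 + 31 = 674)

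| Injections | Longest gap | SAP compliance | Doses taken / due |
|---|---|---|---|
| Full schedule | 28 | 674/674 = 100% | 26/26 |
| Day 7 missed | 28 | 674/674 = 100% | 25/26 = 96.2% |
| Day 14 missed | 28 | 674/674 = 100% | 25/26 = 96.2% |
| Days 7 and 14 missed | 28 (Day 1 to 28 is 27) | 674/674 = 100% | 24/26 = 92.3% |
| One mid-study monthly dose missed | 56 | (674 − 25)/674 = 649/674 = 96.3% | 25/26 = 96.2% |

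The day-based measure tracks the dose count well for a missed monthly dose and not at all for missed loading doses.

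**Variants with Days 7 and 14 missed**

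- Last dose Day 672: 702/702 = 100%, against 25/27 = 92.6% of doses.
- Dosed only on Days 1 and 28: (28 − 1 + 31) = 58, so 58/58 = 100%, against 2/4 = 50% of doses.
- Week 4 dose moved, later doses on schedule: 100% for any day from 25 to 32. That range covers both the ± 1 visit window and the ± 3 injection window. At Day 33 the gap is 32 and the result is 673/674 = 99.85%.
- Week 4 dose missed as well: the Day 1 to Day 56 gap is 55, so (674 − 24)/674 = 650/674 = 96.4%.

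**The case against.** The strongest reply is that missed loading doses are picked up elsewhere. The missed-dose summary in SAP 2.4.1 would place a subject missing both in its 1-3 row, and SAP 2.3.1 tabulates protocol deviations, including COVID-19-related cases of treatment not given. Sites count autoinjectors (Protocol 6.6.2), subjects record missed doses in a diary, and under Protocol 6.7.2 Day 7 is overseen remotely while the Week 2 dose is given on site. All of this stands: the plan does not hide missed doses. But the 1-3 row does not say whether the missed doses were loading or monthly, and none of these sources corrects the 100% compliance row.

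A second reply is that a day-coverage measure and a dose count answer different questions. That is fair for the monthly phase. The SAP's reason for 31 days does not extend to the loading phase, however, and the label covers the whole schedule.

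A reader might infer more than the documents support.

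- **That the formula wrongly penalises adherent subjects.** Monthly doses alternating 3 days early and 3 days late around their scheduled days would score 638/671 = 95.1%. But Protocol 6.7.2 and the SAP attach the ± 3 days to the 4-week interval, so the resulting 34-day intervals are out of window. The pattern also starts on Day 25, outside the Day 28 ± 1 visit window.
- **That the catch-up rule is mishandled.** The rule reads "If one monthly injection is missed by 1 week or less, the subject should take injection as soon as possible". A dose 7 days late gives a 35-day gap and 670/674 = 99.4%. A small deduction for an injection that the protocol itself calls missed is defensible.
- **That exposure duration is also wrong.** The formula credits about 31 days per injection, so Day 1 to Day 28 is not a break in exposure under that definition. Duration of coverage and number of doses are separate quantities.

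**Conclusion.** The point holds for the loading phase. Any subject who omits Day 7, Day 14 or both, takes Week 4 by Day 32 and has no later gap above 31 days is reported as 100% compliant. At Day 644 the overstatement against doses taken is 7.7 percentage points (100 − 92.3) when both are missed; for a subject who stops after Week 4 it is 50 points.

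This rests on counting the on-treatment period inclusively, which is the reading that gives a fully adherent subject exactly 100%, and on taking the similar definition that SAP 2.1.1 mentions for compliance to be the same one. The documents do not say how many subjects are expected to miss loading doses, so the effect on the summary table cannot be sized.

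The consequence is confined to descriptive compliance reporting. It would be wrong to infer that the effectiveness result is at risk: the primary relapse-rate model uses relapse counts with time in study as offset (SAP 2.5.1 and 2.5.2), and time at risk for adverse events runs from first to last dose with interruptions included. Neither uses this percentage.

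**What to change.** In SAP 2.4.1, do one of the following.

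- State that the day-based compliance percentage describes the monthly maintenance phase, from the Week 4 dose. Add one line giving the number and percentage of subjects who received all three loading doses (Days 1, 7 and 14). Subjects who stopped study drug before Day 14 should be identifiable in that line, since the section does not treat early discontinuation as non-compliance.
- Alternatively, report compliance as doses taken over doses due up to the last injection, counting the loading doses.

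Leave the exposure-duration formula unchanged.

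The cost is a wording change and one extra derivation from injection dates that the section already uses. No new data are needed and study conduct does not change. Under the second option reported compliance may be slightly lower.

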2.4.2 Prior, concomitant and post therapies

Analyses described in this section will be performed on the SAF.

2.4.2.1 Concomitant medication

Records on the Concomitant Medications CRF page will be coded using the WHO drug dictionary. All medications will be classified as prior, concomitant or post study drug discontinuation medication as follows:

- Prior medications are defined as drugs taken and stopped prior to first dose of study medication.
- Concomitant medications are defined as drugs taken at least once between first dose and last dose of study medication (including those which were started prior to first dose and continued into the treatment period).
- Post-study drug discontinuation medications will be drugs started after the discontinuation of study medication.

Medications will be categorized into one (and only one) of above classes based on recorded or imputed start and end dates. When incomplete or missing, dates will be imputed according to Novartis standards (details will be given in programming datasets specifications (PDS) document). If both start date and end date are completely missing and medication was not collected on the "Previous MS Disease Modifying Treatment" page, medication will be classified into concomitant medication category.

Medications in each of these 3 categories will be summarized separately by ATC code and preferred term. ATC level 1 and level 3 (e.g., M [Musculo-skeletal system], M01A [anti-inflammatory and anti-rheumatic products, non steroids], etc.) will be used.

Data collected from the Previous MS disease modifying treatment pages or as "Injection related premedication" in the concomitant medication pages will not be included in this summary.

2.4.2.2 Non-drug therapies / procedures

Records on the prior and concomitant non-drug therapies/procedures CRF page will be coded using the MedDRA dictionary. All procedures will be classified as prior, concomitant or post-study drug discontinuation procedure, in the same way as done for concomitant medications. Non-drug therapies/procedures in each of these 3 categories will be summarized separately by system organ class and preferred term.

Imputation rules for start and end dates will follow the same rule as for the concomitant medications.

2.4.2.3 Injection related premedication

Injection related premedication will be identified by subcategory "Injection related premedication" in concomitant medication data set. Injection related premedication will also be summarized separately for each injection up to injection 9 and cumulatively for injections after injection 9 (i.e., injections 10 to last injection) as well as cumulatively for all injections.

For injection 1 summary, the injection related premedication with either start date or end date on the same day as the first injection date will be included and summarized for each of the three protocol specified types and for each combination of the specified types (type 1+ type 2, type 1+ type 3, type 2+ type 3, type 2+ type 3). The three protocol specified types are steroids (type 1), antihistamines (type 2), and antipyretics/analgesics (type 3). The steroids (type 1) will

be identified by category "Steroid". The antihistamines (type 2) will be identified by ATC level 3 "antihistamines for systemic use". The antipyretics/analgesics (type 3) will be identified by ATC level 3 "other analgesics and antipyretics" and "anti-inflammatory and anti-rheumatic products, non-steroids". In summaries for each combination of the specified types, the number and proportion of subjects who took both (or all 3) types of injection related premedication at specified injection will be provided. In addition to this, summary of subjects with no premedication will also be provided.

2.4.2.4 Previous MS disease modifying treatment

Data collected from the previous MS disease modifying treatment pages will be summarized separately.

2.5 Analysis of the primary objective

The primary objective of the study is to determine the effectiveness of ofatumumab 20 mg s.c. administered every 4 weeks in subjects with relapsing forms of MS who have breakthrough treatment response on fumarate-based RMS approved therapies or fingolimod as evaluated by the annualized relapse rate (ARR, based on confirmed relapses) in participants with relapsing MS.

2.5.1 Primary endpoint

The primary endpoint of the study is the annualized relapse rate (ARR, based on confirmed relapses), which is defined as the number of confirmed MS relapses in a year. In the primary analysis, the ARR is estimated based on the FAS using individual relapse count as the response variable with natural log of time in study in years as an offset variable.

Two variables are required for the calculation of the estimated average ARR (excluding covariates):

- The cumulative number of confirmed MS relapses by subject based on EDSS will be derived. All confirmed relapses with a start date on or after the date of first administration of study drug and prior to the efficacy cutoff date will be included in the analysis. Additional details are provided in Section 5.1.4 and Section 5.4.1.
 - The definition of a confirmed MS relapse is one accompanied by a clinically relevant change in the EDSS assessment, i.e. an increase of at least 0.5 points on the EDSS (total) score, or an increase of at least 1 point on at least two Functional scores (FSs), or an increase of at least 2 points on at least one FS, excluding changes involving bowel/bladder or cerebral FS, compared to the last EDSS assessment taken in the absence of (confirmed or unconfirmed) relapse and prior to the current relapse. EDSS obtained on the date as indicated on the Summary of MS Relapse eCRF page will be used. If such EDSS assessment is missing or not meeting the criteria to confirm the relapse, all other EDSS assessments taken within 30 days from the relapse start date (i.e., EDSS assessment date relapse start date <=30) and before the relapse end date (EDSS assessment date < relapse end date) will be checked. If at least one of such available EDSS assessments meets the criteria, the relapse is a confirmed relapse. Otherwise, the relapse is considered an unconfirmed relapse.

• The time-in-study by subject will be used as an offset variable to adjust for the various length subjects have been observed and at-risk of a confirmed MS relapse in the study. Time in study for ARR will be calculated as (end of efficacy cutoff date – first dose date+1)/365.25. Definition of efficacy cutoff date is provided in Section 2.1.

